5.4 Statistical methodology and assumptions

5.4.1 Analysis of continuous data

5.4.1.1 Summary statistics for continuous data

Summary statistics (including N, mean, standard deviation, minimum, lower quartile, median, upper quartile and maximum) will be provided for continuous data by visit and treatment group.

5.4.2 Analysis of binary and categorical data

5.4.2.1 Summary statistics for binary and categorical data

Summary statistics for discrete variables will be presented in contingency tables and will include count and frequency in each category. If applicable, confidence intervals will be derived as well based on the score method including continuity correction (Newcombe 1998):

With z as $(1-\alpha/2)$ -quantile of the standard normal distribution (SAS: $z = PROBIT(1-\alpha/2)$, *n* as total number of subjects (i.e., number of subjects in the denominator), *p* as estimated crude incidence (number of subjects with event / *n*) and q = 1-p

Then the lower limit is

$$L = 100 \times \max\left(0, \frac{2np + z^2 - 1 - z\sqrt{z^2 - 2 - \frac{1}{n} + 4p(nq + 1)}}{2(n + z^2)}\right)$$

and the upper limit is

$$U = 100 \times \min\left(1, \frac{2np + z^2 + 1 + z\sqrt{z^2 + 2 - \frac{1}{n} + 4p(nq - 1)}}{2(n + z^2)}\right)$$

Novartis	Confidential	Page 43 of 45
SAP		Study No. CAIN457P12301

In addition, if L > p then L = p and if U < p then U = p.

For binary response variables the placebo-adjusted response rates including 95% confidence interval will be derived.

SAS code for risk difference:

proc freq data=;

tables response* treatment / riskdiff;

run;

Note the response value should be sorted with '1' ahead of '0'.

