2.11 Patient reported outcomes (PROs)

Patient reported outcomes will be evaluated based on FAS unless otherwise specified.

BASDAI

The following variables will be evaluated:

• BASDAI

For BASDAI, summary statistics of observed data by visit and change from baseline in BASDAI will be provided for each treatment.

BASFI

See Section 5.1 Description of efficacy variables for details.

Patient's global assessment of disease activity (VAS)

Summary statistics of observed data by visit and change from baseline in patient's global assessment of disease activity will be provided for each treatment.

Patient's assessment of back pain intensity (VAS)

Summary statistics of observed data by visit and change from baseline in patient's assessment of back pain intensity will be provided for each treatment.

SF-36

The following variables will be evaluated:

- SF-36 domain scores (based on a scale of 0-100)
- SF-36 PCS (norm-based scores)
- SF-36 PCS (improvement of ≥ 2.5 points, Lubeck 2004)

For the change from baseline in SF-36 summary scores (PCS), summary statistics will be provided using observed data for each treatment regimen.

For the responder analyses, the proportion of responders will be descriptively summarized along with its 95% CI for each randomized treatment based on observed data.

The SF-36 domain scores will be summarized by treatment.

ASQoL

Summary statistics of observed data by visit and change from baseline in ASQoL will be provided for each treatment.

Novartis SAP	Confidential	Page 26 of 45 Study No. CAIN457P12301

PSQI

Summary statistics of observed data by visit and change from baseline in PSQI score will be provided for each treatment.

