2.14 Interim analysis

The primary endpoint analysis was performed after all subjects completed Week 16 or discontinued earlier in order to support regulatory filing.

The investigators, site personnel and monitors continue to remain blinded to the treatment each subject received at randomization until all patients have completed the study (Week 60 Follow-up) and the final database lock has occurred. Additional analyses may be performed to support interactions with health authorities, as necessary.

3 Sample size calculation

An overall type I error (2-sided) of 5% will be used to control type I error. Secukinumab i.v. regimen will be tested versus placebo with respect to the primary endpoint (ASAS40 response at Week 16). A sample size of 250 axSpA patients (200 AS patients and 50 nr-axSpA patients) per group is deemed appropriate to achieve adequate power for the primary and secondary endpoints for this study.

An ASAS40 response rate of about 28.2% for the AS population in the placebo group at week 16 was reported in a published phase III study (CAIN457F2320). The ASAS40 response to secukinumab 150 mg is estimated to be 44.9% in the AS population based on the lower bound of the 90% confidence interval of risk difference from the Meta-analysis of 3 phase III studies (CAIN457F2310, CAIN457F2320 and CAIN457F2308). With 250 patients per treatment group (200 AS patients and 50 nr-axSpA patients), there would be approximately 96% power to detect a treatment difference of 16.7% in ASAS40 response rates between secukinumab and placebo in the evaluation of the primary efficacy hypothesis at Week 16 (Chi Square test, NQuery 7.0). The overall sample size will be 500 patients (400 AS patients and 100 nr-axSpA patients) for a randomization ratio of 1:1.

The estimated power with the chosen sample size for secondary efficacy endpoints based on the pooled results of the same phase III studies (CAIN457F2310, CAIN457F2320 and CAIN457F2308) are summarized in Table 3-1 for binary endpoints and Table 3-2 for continuous endpoints.

Endpoint	Response Rate		Power
	Secukinumab(N = 200 AS + 50 nr-axSpA)	Placebo (N = 200 AS + 50 nr-axSpA)	_
ASAS 5/6	44.2%	19.5%	99%
ASDAS-CRP major improvement	27.8%	6.4%	99%
ASAS20	59.0%	38.4%	99%
ASDAS-CRP inactive disease	13.6%	3.5%	97%
ASAS partial remission	15.2%	5.5%	92%

Table 3-1 Summary of power for binary secondary endpoints

Novartis	Confidential	Page 28 of 45
SAP		Study No. CAIN457P12301

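### SAP 5.4.2.1 puts the confidence limits in percent but clips them against a proportion; coded literally, almost every lower limit falls below 1%

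*SAP*

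**What the plan says.** SAP Section 5.4.2.1 covers binary and categorical summaries. Where an interval is applicable, it states that "confidence intervals will be derived as well based on the score method including continuity correction (Newcombe 1998").

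The section defines p "as estimated crude incidence (number of subjects with event" divided by n, and q as 1−p, so p lies between 0 and 1. It writes the lower limit as 100 × max(0, …) and the upper limit as 100 × min(1, …), so L and U lie between 0 and 100. It closes with the clipping rule: "In addition, if L > p then L = p and if U < p then U = p". Nothing in the section rescales p before that comparison.

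Section 5.4.3.1, for crude incidences, repeats the formulas and the clipping sentence without the factor 100.

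Section 2.11 commits to an interval of this kind for SF-36 PCS responders: "the proportion of responders will be descriptively summarized along with its 95% CI for each randomized treatment based on observed data".

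**The concern.** The rule compares and exchanges quantities on two different scales. A lower limit of 38.57 (percent) will always exceed a p of 0.448 (proportion), so it is replaced by 0.448. The upper limit in percent is never below p, so the upper part of the rule cannot do its job.

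The SAP is the specification against which the programs are validated. As it stands, a program that follows the text produces wrong lower limits, and a program that produces right limits departs from the text. What is at stake is the confidence interval around descriptive response rates. These matter here because SAP Section 2.1 says that data after Week 16 will generally be summarized descriptively.

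**Working it through.** The documents print no numerical limit from this formula, so there is no stated figure to reproduce. The check codes the formula as printed and applies the clip in both ways.

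**Inputs**
- z = 1.96 (unrounded 1.95996, z² = 3.8415), for the 95% level in SAP Section 2.11.
- n = 250 per group, and n = 50 for the nr-axSpA part, from SAP Section 3: "A sample size of 250 axSpA patients (200 AS patients and 50 nr-axSpA patients) per group".
- Illustrative counts. 112/250 and 70/250 lie close to the planning rates of 44.9% and 28.2% in SAP Section 3. They serve only as realistic proportions; the ASAS40 analysis itself does not use this interval. The other counts span the range.

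**Formulas (before the factor 100)**
- l = [2np + z² − 1 − z√(z² − 2 − 1/n + 4p(nq + 1))] / [2(n + z²)]
- u = [2np + z² + 1 + z√(z² + 2 − 1/n + 4p(nq − 1))] / [2(n + z²)]

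**Worked case, 112/250** (p = 0.448, q = 0.552)
- Denominator: 2 × (250 + 3.8415) = 507.683.
- Lower: the root is √250.926 = 15.841. The numerator is 224 + 3.8415 − 1 − 1.95996 × 15.841 = 195.794. So l = 0.38566, or 38.57%.
- Upper: the root is √251.342 = 15.854. The numerator is 224 + 3.8415 + 1 + 1.95996 × 15.854 = 259.914. So u = 0.51196, or 51.20%.
- Clip on one scale: 0.38566 < 0.448 < 0.51196, so nothing changes.
- Clip as written in 5.4.2.1: L = 38.57 > 0.448, so L becomes 0.448. U = 51.20 is not below 0.448, so it stays.

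**Other cases**

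| Events/n | Consistent scale, % | As written in 5.4.2.1 |
|---|---|---|
| 112/250 | 38.57 to 51.20 | 0.448 to 51.20 |
| 70/250 | 22.61 to 34.08 | 0.28 to 34.08 |
| 148/250 | 52.81 to 65.30 | 0.592 to 65.30 |
| 16/250 | 3.82 to 10.38 | 0.064 to 10.38 |
| 2/250 | 0.14 to 3.17 | 0.008 to 3.17 |
| 30/50 | 45.20 to 73.27 | 0.6 to 73.27 |

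**All counts.** For n = 50, 100, 200, 250 and 500, every count x from 0 to n was run.
- As written, the lower clip fires at every x, so L always equals p. It is below 1 for every x < n and equals 1 at x = n. The upper clip never fires.
- On one scale, the clip acts only at x = 0 and x = n. At 0/250 the raw lower limit is 0.036%, above the estimate of 0, and is set to 0. At 250/250 the raw upper limit is 99.96%, below the estimate of 100%, and is set to 100%.

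The rule is therefore a guard for the two extreme counts. As written it spoils the lower limit everywhere except x = 0, where the value 0 is right on either scale, and it leaves the case x = n unrepaired.

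**The case against.** The best counter-argument is about weight, since the arithmetic is not in doubt. Section 5.4.3.1 prints the consistent form, and a guard for extreme counts cannot sensibly be meant to overwrite every lower limit, so there is only one reasonable reading. An interval of 0.448 to 51.20 around 44.8% would be noticed at the first review of output, and nothing in the documents shows that the rule was coded this way.

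The reach is also narrow:
- The Week 16 primary and secondary endpoints are tested by logistic regression or MMRM (protocol 12.4.2 and 12.5.1), and this SAP does not repeat those analyses (2.5 and 2.6).
- Safety intervals use 5.4.3.1.
- The placebo-adjusted response rates come from a standard risk-difference procedure.
- The one use visible in the SAP is the SF-36 PCS responder proportion. Wider use in by-visit response rates is plausible: after the PSQI entry, protocol 12.5.7 says that other binary endpoints may be summarized with 95% intervals. The public SAP text does not confirm it.

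All of this stands, and it limits the consequence. It does not make the stated rule correct. A specification that has to be overridden to give the right answer should be corrected.

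**Conclusion.** The concern holds. The clipping rule in SAP 5.4.2.1 mixes percent and proportion and is wrong as written. Under literal coding, the lower limit equals p for every count at all five sample sizes checked. At the planned group size, a lower limit that should be 22.61% or 38.57% would be reported as 0.28 or 0.448. Where the correct limit is already below 1%, the distortion is small: 2/50 gives 0.04 instead of 0.70%.

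This size is conditional on the text being programmed literally; the documents do not show whether it was. The effect is confined to descriptive intervals for single proportions. No hypothesis test, multiplicity step, sample size or safety interval depends on it. It should be corrected, but it does not threaten the trial's main result.

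**What to change.** Remove the factor 100 from both limits in 5.4.2.1, clip on the proportion scale as 5.4.3.1 does, and convert to percent afterwards. Equivalently, keep the factor and clip L down to 100p when L exceeds 100p, and U up to 100p when U is below 100p.

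Then run the program once at x = 0, at x = n and at one middle value. With n = 250 the results should be 0% to 1.89%, 98.11% to 100%, and, for 112 events, 38.57% to 51.20%.

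The cost is one line of SAP text and a short check of the program. There is no downside.

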12.4.2 Statistical model, hypothesis, and method of analysis

The estimand for primary endpoint is defined as follows:

- A. Population: defined through appropriate inclusion/exclusion criteria to reflect the targeted axSpA population (AS and nr-axSpA)
- B. Variable: composite of remaining on the study and on randomized treatment through 16 weeks and achieving ASAS40 response at 16 weeks
- C. Intercurrent event: the intercurrent event is captured through the variable definition
- D. Population-level summary: difference in proportions of responders between the secukinumab and placebo arms

The statistical hypothesis for ASAS40 being tested is that there is no difference in the proportion of subjects fulfilling the ASAS40 criteria at Week 16 in the secukinumab i.v. regimen versus placebo regimen.

Let p_0 denote the proportion of ASAS40 responders at Week 16 for placebo regimen and p_1 denote the proportion of ASAS40 responders at Week 16 for secukinumab i.v. regimen.

In statistical terms, $H_1: p_1 = p_0$, $H_{A1}: p_1 \neq p_0$, i.e.,

H_1 : secukinumab i.v. regimen is not different to placebo regimen with respect to ASAS40 response at Week 16

The primary analysis will be conducted via logistic regression with treatment and stratification factor (disease condition) as factors and weight as a covariate. Difference in marginal response proportions with p-value and 95% confidence interval (CI) will be presented comparing secukinumab i.v. regimen to placebo.

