2.2.2 Subgroup of interest

The primary and secondary endpoints will be analyzed by disease condition (AS and nr-axSpA). Analyses by previous use of TNF- α inhibitor may also be provided for overall axSpA population.

Novartis	Confidential	Page 13 of 45
SAP		Study No. CAIN457P12301

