2.5 Analysis of the primary objective

The primary efficacy variable is response to treatment according to the ASAS40 criteria at Week 16 in patients with active axSpA (AS and nr-axSpA).

The analysis of primary variable at Week 16 will not be reproduced for the Final Analysis.

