2.6 Analysis of secondary objectives

The secondary efficacy variables include,

- response to treatment at Week 16 according to the ASDAS-CRP major improvement criteria
- change from baseline in BASDAI at Week 16
- response to treatment at Week 16 according to the ASAS 5/6 criteria
- change from baseline in total BASFI score at Week 16
- change from baseline in SF-36 PCS at Week 16
- change from baseline in ASQoL at Week 16
- change from baseline in hsCRP at Week 16
- response to treatment at Week 16 according to the ASAS20 criteria

Novartis	Confidential	Page 15 of 45
SAP		Study No. CAIN457P12301

- response to treatment at Week 16 according to the ASDAS-CRP inactive disease criteria
- response to treatment at Week 16 according to the ASAS partial remission
- change from baseline in PSQI at Week 16

The analysis of secondary variables at Week 16 will not be reproduced for the Final Analysis.

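### The SAP's PROC FREQ line for the risk difference has rows and columns swapped, so it does not give the placebo-adjusted response rate (minor; confirmatory results unaffected)

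*SAP*

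**What the plan says.** SAP 5.4.2.1 deals with descriptive output: "Summary statistics for discrete variables will be presented in contingency tables and will include count and frequency in each category". It then sets a target: "For binary response variables the placebo-adjusted response rates including 95% confidence interval will be derived". The code offered for the risk difference is a PROC FREQ step whose only analysis statement is "tables response* treatment / riskdiff". A note under the code asks for response level 1 to be sorted ahead of level 0. Neither the code nor the note gives an order for the treatment levels.

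The confirmatory effect measure is defined elsewhere. Protocol 12.4.2 specifies logistic regression for ASAS40 and says: "Difference in marginal response proportions with p-value and 95% confidence interval (CI) will be presented comparing secukinumab i.v. regimen to placebo". Protocol 12.5.1 also uses logistic regression for the binary secondary endpoints. The SAP covers the final analysis. Section 2.5 says "The analysis of primary variable at Week 16 will not be reproduced for the Final Analysis", and section 2.6 says "The analysis of secondary variables at Week 16 will not be reproduced for the Final Analysis". SAP 2.2.2 calls for the primary and secondary endpoints to be analysed by disease condition (AS and nr-axSpA) but names no method.

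**The concern.** The text and the code in the same subsection specify different quantities. The text asks for P(response | secukinumab) − P(response | placebo). The code returns P(a given treatment | responder) − P(the same treatment | non-responder). Sorting response 1 first only decides which row comes first; it does not move response to the columns. The sign of the result also depends on which treatment column is read.

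A table built from this line would show a wrong estimate and a wrong interval under a risk-difference label. For endpoints with a response rate near one half the wrong figure looks believable, so a check on ASAS20 or ASAS40 might not catch it. For the rarer endpoints, ASDAS-CRP inactive disease and ASAS partial remission, the overstatement is large.

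**Working it through.** **Inputs.** From SAP section 3 and Table 3-1 (the same as Protocol 12.8): 250 per arm, 1:1 allocation, and the planning response rates. The documents give no numerical output for the code itself, so the planning rates serve as the illustration. Row-minus-row behaviour is how PROC FREQ works; the documents do not state it.

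**Check of the planning rates.** For ASAS40 at 44.9% vs 28.2%, 250 per arm and two-sided 5%, the chi-square power is 97.4% without and 96.8% with continuity correction. The stated figure is approximately 96%, so the inputs are consistent with the plan.

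**Formula.** Let p1 and p0 be the secukinumab and placebo response rates, and pbar = (p1 + p0)/2. With equal arms,

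- intended: p1 − p0
- as coded: p1/(p1 + p0) − (1 − p1)/[(1 − p1) + (1 − p0)] = (p1 − p0)/[4·pbar·(1 − pbar)]

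The coded value is zero exactly when the true difference is zero. The ratio of coded to true depends only on pbar: it is 1 at pbar = 0.5 and grows as pbar moves away from 0.5.

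**Worked case, ASDAS-CRP inactive disease.** p1 = 0.136 and p0 = 0.035, so the true difference is 0.101. Coded: 0.136/0.171 − 0.864/1.829 = 0.795 − 0.472 = 0.323. Check: pbar = 0.0855 and 1/(4 × 0.0855 × 0.9145) = 3.20.

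**All binary endpoints**, in percentage points with Wald 95% CI, 250 per arm. The coded column takes secukinumab as the treatment column read.

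| Endpoint | p1, p0 | True difference | Coded row shares | Coded difference | Ratio |
|---|---|---|---|---|---|
| ASAS20 | 59.0%, 38.4% | 20.6 (12.0 to 29.2) | 60.6%, 40.0% | 20.6 (12.0 to 29.2) | 1.00 |
| ASAS40 | 44.9%, 28.2% | 16.7 (8.4 to 25.0) | 61.4%, 43.4% | 18.0 (9.1 to 26.9) | 1.08 |
| ASAS 5/6 | 44.2%, 19.5% | 24.7 (16.8 to 32.6) | 69.4%, 40.9% | 28.4 (19.6 to 37.3) | 1.15 |
| ASDAS-CRP major improvement | 27.8%, 6.4% | 21.4 (15.1 to 27.7) | 81.3%, 43.5% | 37.7 (28.2 to 47.3) | 1.76 |
| ASAS partial remission | 15.2%, 5.5% | 9.7 (4.4 to 15.0) | 73.4%, 47.3% | 26.1 (13.2 to 39.0) | 2.69 |
| ASDAS-CRP inactive disease | 13.6%, 3.5% | 10.1 (5.3 to 14.9) | 79.5%, 47.2% | 32.3 (19.4 to 45.2) | 3.20 |

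**Small-subgroup illustration.** Assume the line were used for nr-axSpA, with 50 per arm and the same planning rates, giving about 7 vs 2 inactive-disease responders.

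- True: 7/50 − 2/50 = 0.100, SE 0.0564, Wald CI −1.0 to 21.0 points.
- Coded: 7/9 − 43/91 = 0.778 − 0.473 = 0.305, SE 0.148, Wald CI 1.5 to 59.6 points.

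Here the coded Wald interval excludes zero and the true one does not. This contrast depends on the Wald method. Newcombe intervals are −1.8 to 22.5 (true) and −3.5 to 49.3 (coded), and both include zero. The chi-square test of association is the same for both layouts (p = 0.081). Transposition therefore distorts the estimate and its interval but does not create evidence of an effect.

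**The case against.** The strongest reply is that nothing visible uses the line. Under SAP 2.1, comparison with placebo is confined to the first 16 weeks, and later data are generally summarised descriptively by treatment sequence. The Week 16 primary and secondary analyses are not repeated. The SF-36 responder summary in SAP 2.11 gives a proportion per treatment, not a difference. The prose in 5.4.2.1 also states the target correctly, and *placebo-adjusted* fixes its direction. The code is a skeleton without a dataset name that a programmer has to complete. Printed row shares such as 79.5% and 47.2% for inactive disease would look odd to anyone who expects response rates of 13.6% and 3.5%. The nr-axSpA illustration borrows rates from AS studies, and its change in conclusion appears only with the Wald interval.

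Most of this stands as a limit on reach. Any consequence is conditional on a table being made from the line, and the subgroup example should be read only as an illustration. The missing treatment order is a secondary drafting point. None of this makes the code correct. The sentence promising these rates is current text, this is the only risk-difference code printed in the SAP, and SAP 2.2.2 leaves the subgroup method open. The visible section numbers pass from 2.6 to 2.8, so a call to the template in text that is not shown cannot be ruled out either way.

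**Conclusion.** The concern holds and is minor. Followed as printed, the code gives the wrong unadjusted difference and the wrong confidence interval. At planning rates the difference is overstated by a factor between 1.00 (ASAS20) and 3.20 (ASDAS-CRP inactive disease).

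The primary result, the testing sequence and the type I error are unaffected, because those analyses rest on logistic regression.

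The sizes assume the planning rates, equal arms, expected counts and Wald intervals; observed rates would give other ratios through the pooled rate. The SAP used for the Week 16 report is not among the documents, so it is not known whether the same line produced any Week 16 table.

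**What to change.** Replace the statement in SAP 5.4.2.1 with `tables treatment*response / riskdiff;`. Extend the note to say that secukinumab is the first row and response 1 the first column. With that order the column 1 difference is secukinumab minus placebo, as the text intends, and the planning rates return the true differences tabulated above.

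Then check whether the old line was used for any unadjusted Week 16 output, including tables by disease condition, and rerun those tables if it was. The cost is one line of code, one sentence in the note and a check of existing output. Data, design and testing do not change.

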5.4.3 Crude incidence and related risk estimates

5.4.3.1 Crude incidence and 100*(1-α)% confidence interval

For *n* subjects, each at risk to experience a certain event with probability π , the crude incidence is estimated as p=x/n, where *x* is the number of subjects with the event.

Absolute and relative frequencies will be displayed as well as 95% confidence interval for the relative frequency based on the score method including continuity correction (Newcombe 1998).

With z as $(1-\alpha/2)$ -quantile of the standard normal distribution (SAS: $z = PROBIT(1-\alpha/2)$, *n* as total number of subjects (i.e., number of subjects in the denominator), *p* as estimated crude incidence (number of subjects with event / *n*) and *q*=1-*p*.

Then the lower limit is

$$L = \max\left(0, \frac{2np + z^2 - 1 - z\sqrt{z^2 - 2 - \frac{1}{n} + 4p(nq + 1)}}{2(n + z^2)}\right)$$

and the upper limit is

$$U = \min\left(1, \frac{2np + z^2 + 1 + z\sqrt{z^2 + 2 - \frac{1}{n} + 4p(nq - 1)}}{2(n + z^2)}\right).$$

In addition, if L > p then L = p and if U < p then U = p.

If appropriate, an exact $100^{*}(1-\alpha)^{\%}$ confidence interval (Clopper-Pearson, 1934) will be obtained by using the SAS procedure PROC FREQ with the EXACT BINOMIAL statement. However, the confidence interval derived via the score method including continuity correction will be the default in safety analyses.

Novartis	Confidential	Page 44 of 45
SAP		Study No. CAIN457P12301

